1.3 Schedule of Activities

Timeline for the Thrive study

Schedule of Assessments for the Thrive Study

	Screen	Consent	Baseline (T1)	Tech 1 (T2)	Tech 2 (T3)	Tech 3 (T4)	Tech 4 (T5)	Post-study (T6)	1 Mo (T7)	3 Mo (T8)
Eligibility	X									
Randomization		X								
Informed Consent		X								
Demographics		X								
Outcome Evaluations*										
Technology sessions - Positive Engagement (self-report)				X	X	X	X			
Technology sessions - Positive engagement (behavioral coding)				X	X	X	X			
Quality of Life			X	X	X	X	X	X	X	X
Mental Health			X	X	X	X	X	X	X	X
Thriving			X					X	X	X
Loneliness and social connection			X	X	X	X	X	X	X	X
Caregiver Guilt			X	X	X	X	X	X	X	X
Family bonding			X	X	X	X	X	X	X	X

* The outcomes listed above refer to general constructs rather than specific measures. Most outcomes will be measured using more than one self-report and/or behavioral assessment.

2 Introduction

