The positive engagement that shared VR creates should, in turn, improve the quality of life of residents and their adult children. **For residents with and without cognitive impairments, quality of life means being able to maintain important family connections, have control over their lives, and feel as if their lives still have meaning.**²¹ . We are conceptualizing quality of life as general happiness with one's life and also low levels of social isolation/loneliness, positive mental health, and the ability to thrive. Rendever could be a crucial way to connect residents with their adult children, reducing social isolation and

improving the mental and relational health of everyone involved. Virtual reality allows older adults to continue to grow, experience new sensations, travel, and live life outside senior living communities. This may be especially true if VR allows residents with varying levels of cognitive impairment to connect to their past and do things they can no longer do because of cognitive and/or physical limitations. Because of the immersive nature of VR, Rendever should be more effective at promoting these processes compared to other means, such as video chat. In Phase II, we also want to show that using Rendever has a longer-term impact beyond the moments right after its use. Importantly, adult children who live in another state might not have as many opportunities to engage in activities with their parents compared to a sibling who lives nearby. Shared VR experiences can create common ground and give the dyad something exciting to talk about that is unique to that relationship, fostering a social bond in ways that last beyond the VR sessions. Therefore, our first aim and hypotheses are:

AIM1: Determine whether Rendever (vs. control) improves **quality of life** for residents and their adult children who live at a distance.

- **H1a:** Residents and adult children in the VR condition (vs. control) will show significantly **greater improvements in quality of life** (reductions in loneliness, improvements in mental health and thriving) both concurrently and over time (relative to baseline).
- **H1b:** The positive effects of the VR condition (vs. control) on residents' and adult children's **quality of life** will be **mediated by** (explained by) increases in **positive engagement** (positive affect, engagement with the technology and with the adult child while using it, emotional closeness with the adult child).

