A second aim of Phase II is to continue to determine the level of cognitive impairment for which Rendever is most beneficial. Virtual reality has been used successfully with older adults with MCI and mild to moderate AD/ADR to enhance cognition, navigation, spatial orientation, attention, spatial memory, mobility, and balance. Research with residents with and without dementia suggests that VR is enjoyable and can induce positive affect. For instance, virtual environments have been found to increase joy and relaxation in residents and reduce anxiety and sadness.¹⁶ Researchers have also tested sustained attention while using VR, versus a paper version of the task, among residents with MCI and dementia. Residents, regardless of the level of cognitive impairment, found the VR enjoyable, reported high feelings of security and low levels of discomfort and anxiety, and preferred the VR over the paper condition. Interestingly, residents with greater apathy preferred the VR condition the most and reaped the greatest benefits. Virtual reality has also been used with older adults without cognitive impairments for reminiscence therapy and shown that the number of memories generated is greater with familiar than unfamiliar settings.²² Other researchers have found that VR can enhance autobiographical memory in older adults with MCI²³ and that VR can improve memory in older adults with MCI more than music therapy. **Little research, however, has examined the impact of VR on older adults' social well-being, particularly among residents with dementia. What has been missing from VR is sophisticated networking and livestreaming functions, which Rendever provides.** The ability for residents to travel back in time to their childhood home and other memorable places with their adult child while sharing stories together should facilitate positive engagement for both of them.

We already demonstrated in Phase I that Rendever can be used safely with residents with MCI and mild to moderate AD/ADR and that residents loved the experience, regardless of their level of cognitive impairment. Our Phase I results suggest that Rendever is beneficial for residents with MCI and mild to moderate dementia, especially if it involves reminiscence therapy. We also found in our automated and human coding that the higher the MMSE-2 score (or the less dementia), the more engaged the resident

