experiences naturally (and let the photos and travel experiences be the prompts), to listen to the resident, allow the resident to share his/her feelings and memories, and to not force memories the resident might not have or attempt to change their memories. Some residents with dementia might get upset if they fail to recognize themselves, others, or their family home in a photo. In such cases, the family member will be asked to avoid asking the resident to recall specific people or names, to guide them toward more positive emotions, and try to refrain from telling the resident that he/she is wrong about a memory of an event. The family member will also be encouraged to pause and take off their headset (or take a break from the Zoom session) if they are experiencing negative feelings or potential physical side effects. Each week, the researcher will briefly check in with the adult child and resident separately about their experiences, which will include assessing how they are feeling and answering any questions or concerns they might have as a result of the session. In the Phase 1 pilot study, *no such concerns were raised.*

The researcher conducting each VR session will also carefully monitor how the adult child is communicating with the resident. If a resident becomes uneasy, the researcher will check in with them, redirect the conversation if needed, or stop the conversation if it becomes problematic. Most older adults have satisfying relationships with their friends and family, but some do not.³² Dementia can also strain those relationships. Harmful family relationships will be screened for and deemed ineligible to participate ahead of time, but family dyads with a range of relational experiences will be allowed to participate. Research shows that shared activities can bring residents and family members emotionally closer to each other and improve their communication.^{24, 25} The VR/Zoom activities should induce positive emotions and feelings of connection over time because of the novel, shared experiences. There is also likely a selection bias in that family members who already have a good relationship are more likely to participate in the study than those who do not. Nevertheless, if a research assistant observes unpleasant interpersonal dynamics, the assistant will contact the PIs, who will check in with participants and decide whether the study needs to stop.

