4.1 Overall Design

Purpose of the clinical trial: The virtual reality (VR) program, Rendever, enables older adults in senior living communities to maintain important family relationships, engage fully with life, and reconnect with their past, regardless of physical location, through its advanced networking and live streaming capabilities. This Phase II project will continue to refine the long-distance features of Rendever, while expanding the scientific goals of the project by testing the immediate and longer-term impact of Rendever on the quality of life of residents and their adult children in an experimental design. The study will also continue to investigate whether residents' responses to the VR depend upon their level of cognitive impairment.

Study Design: The design of this study is a 2 (Intervention Group: Virtual Reality vs. Active Control) x 2 (Level of Cognitive Impairment: MCI vs. AD/ADR) x Time (7 time points) design. Participants will be older adults (age 50+) with mild cognitive impairments (MCI) or mild to moderate Alzheimer's Disease or related dementias (AD/ADR) who reside in senior living communities, and an adult child who lives at a distance. Residents will participate from a private room located in their senior living community. Adult children (age 18+) will participate from their own home, at least 45 minutes driving distance away. Resident-adult child dyads will be randomly assigned to an intervention group (Virtual Reality vs. Control) using a random number generator. Dependent variables will include measures of quality of life (quality of life, thriving, depression, mental health, positive and negative affectivity, loneliness, and social connection), family bonding (closeness, satisfaction, communal coping), and caregiver guilt (guilt, stress, and burden) assessed through surveys and interviews over the 4-month study period. Secondary outcome measures will include positive engagement *during the technology sessions* (positive affect, engagement with the technology and with the adult child while using it, emotional closeness) measured through surveys, interviews, and observational methods during the intervention phase of the study.

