9.4.2 Analysis of the Primary Endpoint(s)

The longitudinal dataset including survey and observational data will enable both between and within participant tests of the hypotheses outlined. The data collected will have three levels of nestedness: repeated measures over time (Level 1), nested within person (either older adult or adult child; Level 2), nested within intervention group (VR vs. Control; Level 3). For some analyses (e.g., Aim 1 and 2), we would not estimate the dyad together since, for example, we do not have specific hypotheses about how the resident and the adult child will differ from each other over time and because the parent and adult child will complete somewhat different measures. Outcomes related to Aim 1 and Aim2 will be assessed with linear mixed-models and, where appropriate, with multilevel structural equation modeling (ML-SEM). ML-SEM merges traditional multilevel modeling, which can accommodate hierarchical data, with structural equation modeling (SEM) techniques, which can accommodate multiple outcomes and mediators, as well as latent variables. Therefore, the analytic approach for some hypotheses tests (e.g., tests of mediation and tests of dyadic models) will be multilevel structural equation modeling (ML-SEM) in Mplus (or R) to simultaneously estimate a within- and between-person model, accounting for individual change over time and the treatment effect at the between-person level. Using parameter constraints, analyses will examine concurrent differences between VR and control (e.g., at a given time point) as well as sustained gains across VR and control using an approach similar to contrast coding.

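### The H1b and RQ2 mediation models name no adjustment for common causes of engagement and outcome, so the indirect effect can be biased

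*Combined protocol and SAP*

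**What the plan says.** - **Hypotheses (2.1).** The rationale for Aim 1 is that "The positive engagement that shared VR creates should, in turn, improve the quality of life of residents and their adult children". H1b attributes the VR effect on quality of life, in residents and adult children, to increases in positive engagement. It defines engagement as positive affect, "engagement with the technology and with the adult child while using it, emotional closeness with the adult child". RQ2 asks whether any difference by cognitive level is mediated in the same way.
- **Timing of the mediator (1.3, 4.1).** The schedule marks both session-engagement rows, self-report and behavioural coding, at T2 to T5 and neither at T1. Section 4.1 has engagement "measured through surveys, interviews, and observational methods during the intervention phase of the study".
- **Model (9.4.2).** Mediation is tested by multilevel structural equation modelling, "accounting for individual change over time and the treatment effect at the between-person level". Section 9.4.1 lists mediation models among the secondary analyses.
- **Adjustment.** Sections 9.4.1 to 9.4.3 name no covariate for the mediator or outcome equation, state no assumption about confounding between engagement and outcome, and plan no sensitivity analysis for it.
- **What is measured beforehand.** Family bonding, which includes closeness (4.1), is marked at T1 in 1.3. Affectivity is a primary endpoint (9.1), and 6.1.2 takes the primary measures at baseline. MMSE-2 is given at screening (5.5, 8.1).

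**The concern.** Dyads are randomised, so arm does not vary within a dyad, and the treatment effect sits between persons. The indirect effect is the product of two paths. The first, arm to engagement, is a randomised comparison. The second, engagement to outcome, compares people who engaged more with people who engaged less, and nothing was randomised there. A within-person level in the model does not change this.

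The protocol itself points to common causes. Dyads differ in closeness on entry: "family dyads with a range of relational experiences will be allowed to participate" (2.3.3). The theory in 2.1 links well-maintained relationships to more engaged communication, and family bonds to better health. Phase I found that "the higher the MMSE-2 score (or the less dementia), the more engaged the resident" was, in one type of session. If families who are already close or cheerful both engage more and score better, the second path can be non-zero although engagement does nothing, and the product would be read as the mechanism of VR. What is at stake is the explanation attached to Aim 1, not whether VR works.

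**Working it through.** **The plan's own figure.** There is none for the mediation test. The 85% power at d = 0.2 in 9.2 concerns treatment and moderation effects. Its correlations and variances are not given, so it can be neither confirmed nor refuted, and nothing below depends on it.

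**Inputs from the documents.** 192 dyads allocated 1:1 with 15% attrition: 192 × 0.85 = 163. The realised figures in 1.2 are compatible: 372 / 2 = 186 dyads, less 20, gives 166, and the loss of 12 further individuals leaves 154 to 166 on either side of the dyad. The direct VR effect is set at 0.2 SD.

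**Assumed, because not given.** Two-sided 5% tests; VR effect on engagement a = 0, 0.2 or 0.5 SD; a T1 trait U (closeness or affect) with loading r = 0.3 or 0.5 on both engagement and outcome; an extra effect c of U on the later outcome, 0 (stable trait) or 0.2 (trait predicts change); 60% of outcome variance stable.

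**Model, with no effect of engagement on outcome.**
- Engagement: M = aX + rU + noise, with variance 1 within arm.
- Baseline outcome: Y0 = rU + other stable part + noise, with variance 1.
- Later outcome: Y1 = 0.2X + (r + c)U + the same stable part + noise.

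Mediation is declared when both paths are significant. There were 2000 runs per cell, so the Monte Carlo standard error is at most √(0.5 × 0.5 / 2000) = 1.1 points.

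**Expected spurious indirect effect, with a = 0.5 and r = 0.5.**
- Post-only outcome: a·r·(r + c). For c = 0, 0.5 × 0.5 × 0.5 = 0.125 (simulated 0.126). For c = 0.2, 0.5 × 0.5 × 0.7 = 0.175 (0.176).
- Change score: a·r·c. For c = 0 it is 0 (0.000). For c = 0.2, 0.5 × 0.5 × 0.2 = 0.050 (0.051).
- Baseline outcome as covariate: a·[r(r + c) − r²(0.6 + rc)] / (1 − r⁴). For c = 0, 0.5 × (0.25 − 0.15) / 0.9375 = 0.053 (0.054). For c = 0.2, 0.5 × (0.35 − 0.175) / 0.9375 = 0.093 (0.094).
- Baseline outcome plus the T1 trait measured with reliability 0.8: simulated 0.017 (c = 0) and 0.028 (c = 0.2).

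**False-mediation rate, % of trials.**

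| a | r | Trait | Post-only | Change score | Baseline outcome only | Baseline outcome + T1 trait (reliability 0.8) | Baseline outcome + exact trait |
|---|---|---|---|---|---|---|---|
| 0.2 | 0.3 | stable | 5.8 | 1.4 | 2.6 | 1.5 | 1.6 |
| 0.2 | 0.3 | predicts change | 10.0 | 3.4 | 6.4 | 1.7 | 1.7 |
| 0.2 | 0.5 | stable | 22.2 | 1.4 | 10.7 | 2.4 | 1.4 |
| 0.2 | 0.5 | predicts change | 24.9 | 7.6 | 20.6 | 4.0 | 1.8 |
| 0.5 | 0.3 | stable | 19.3 | 4.9 | 8.6 | 4.6 | 4.6 |
| 0.5 | 0.3 | predicts change | 39.0 | 12.0 | 24.0 | 6.3 | 5.6 |
| 0.5 | 0.5 | stable | 81.2 | 4.8 | 35.2 | 7.2 | 5.2 |
| 0.5 | 0.5 | predicts change | 88.5 | 25.6 | 69.5 | 12.0 | 5.0 |

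With a = 0, no model exceeded 4.6%: without a VR effect on engagement there is no excess.

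**The case against.** **The plan looks at change.** H1a concerns improvement relative to baseline, and 9.4.2 refers to individual change over time. A reader might infer from the post-only column that false mediation in four trials out of five is to be expected. The documents do not support that: with a change score and a stable trait the rate never exceeds 5%. This objection stands as a limit on size. It does not settle the matter, because 9.4.2 does not say how T1 enters the mediation model. The baseline outcome alone leaves up to 35% with a stable trait, and a change score leaves up to 26% if the trait also predicts change.

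**The inputs could be generous.** The only VR-versus-control effect size in the documents is d = 0.2. With that value for engagement, no model exceeds 25%. No document supplies the correlations. Against this, 2.1 predicts more engagement with VR than with video chat, so a positive first path is the sponsor's own expectation.

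**Engagement is not wholly without a baseline.** A reader might infer that it is. Closeness and affect, two of its named components, are measured at T1. Only in-session engagement is not, and it cannot exist before a session. RQ2 and section 3 already speak of differences between groups, so the word increases in H1b is a minor matter of wording.

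**The evidence on cognition is mixed.** Right after the MMSE-2 finding, 2.1 reports that residents with dementia felt more immersed than those with MCI. It also says Phase I was too small to compare the two groups on quality of life. Cognitive group is a randomisation stratum (6.3) and the moderator in RQ2. Section 2.3.3 screens out harmful relationships and expects good ones to be over-represented, which narrows the spread in closeness. These points weaken the individual confounders but do not remove them.

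**Silence is not exclusion, and mediation is secondary.** Both are true, and they limit the weight of the point. Silence still leaves the adjustment set to be chosen after the data are seen.

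**Conclusion.** The point holds as a free improvement. The plan names no adjustment for common causes of engagement and outcome in the H1b and RQ2 models, so a significant indirect effect cannot separate engagement that improves quality of life from families who engage more and would have scored better anyway. The bias is possible and conditional: it needs a VR effect on engagement, a trait that drives both engagement and outcome, and a model that leaves that trait unadjusted. Depending on those assumptions, the false-mediation rate runs from nominal to nearly 90%, and the documents do not fix where in that range this trial lies. The firmer result is the comparison between models: adding T1 closeness or affect to the baseline outcome gave 12% or less in every scenario. A reader should not infer that the VR effect itself is confounded. H1a and the effect of arm on engagement remain protected by randomisation.

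**What to change.** In 9.4.2, for every H1b and RQ2 model:

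1. Include the T1 value of the outcome, T1 positive and negative affect, T1 family bonding (closeness) and screening MMSE-2 as covariates in both the mediator and the outcome equation.
2. For in-session engagement, describe the mediator as the between-arm difference in T2 to T5 engagement, not as an increase.
3. Report a sensitivity analysis giving the residual mediator-outcome correlation that would remove the indirect effect. It is needed because covariates measured with error reduce the bias without removing it: at reliability 0.8, up to 12% false mediation remained, against about 5% with the trait measured exactly.

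The cost is SAP wording and a few extra model terms, with no new data collection. The reported indirect effect may become smaller. Section 1.2 already reports attrition over the whole trial, so the change should be dated before the mediation models are run, or labelled as a later addition.

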6.1.2 Administration and/or Dosing

All residents will participate in their study sessions and surveys from a private room in their senior living community. All adult children will complete their study sessions and all surveys virtually. Resident-adult child dyads will complete a consent form and three brief background measures (on physical health and social isolation), a baseline survey the week before the technology sessions, followed by 4 virtual reality (VR) or Zoom experiences (described below) once a week for four consecutive weeks, a post-study survey, and then a 1- and 3-month follow-up survey. Each VR/Zoom session will last approximately 30 minutes, but could be longer if participants desire. Surveys will occur immediately after each VR/Zoom session, as well as an interview after the last VR/Zoom session (see the table below). All residents will receive the same surveys and all of the adult children will receive the same surveys (the adult children have slightly different measures, such as caregiver guilt, which residents do not complete). All primary outcome measures will be asked at four key time points (baseline, 1-week post-intervention, 1-month post-intervention, and 3-months post-intervention). The surveys after each technology session will be much briefer, focusing on secondary outcomes including experiences with the technology, affective states, and how they felt about their relationship with their family member while using the technology and during the past week. After the study is completely over, the adult children will be emailed a brief, three-minute commercialization survey that asks them the extent to which they would use the product at home if it were available and how much they would pay for it.

All of the VR/Zoom sessions with the residents will occur in person. All interviews will be audio-taped and the VR/Zoom sessions with the residents will be audio and video-taped. The videotapes will be coded later with human and automated coding to assess residents' bodily and conversational engagement while using the VR. All of the audiotapes will be transcribed. The follow-up interviews will be collected face-to-face with the residents and via the telephone for the adult children. The surveys will be conducted in person with the older adult residents. The adult children will complete all of their surveys online through clicking on a Qualtrics link sent to their email.

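### H1b's mediator shares positive affect with the outcome and may be reported at the same session, so if VR raises engagement a significant indirect effect cannot be read as mediation

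*Combined protocol and SAP*

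**What the plan says.** **Mediator.** H1b in Section 2.1 defines positive engagement as "positive affect, engagement with the technology and with the adult child while using it, emotional closeness with the adult child". Section 4.1 repeats the definition and gives its sources: "positive affect, engagement with the technology and with the adult child while using it, emotional closeness) measured through surveys, interviews, and observational methods". The Section 1.3 schedule has two engagement rows, self-report and behavioral coding, both marked at T2-T5 only.

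**Outcome.** H1a words quality of life narrowly: "reductions in loneliness, improvements in mental health and thriving". Section 4.1 words it more widely: "quality of life (quality of life, thriving, depression, mental health, positive and negative affectivity, loneliness, and social connection". Section 9.1 lists positive and negative affectivity as a primary endpoint for both members of the dyad. Closeness sits in another domain, "family bonding (closeness, satisfaction, communal coping". However, the third objective in Section 3 asks whether immediate engagement and family bonding mediate effects on parent and adult child outcomes generally, and family relationships are among those outcomes.

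**Timing.** H1a is to be tested "both concurrently and over time (relative to baseline"). The Section 1.3 schedule marks quality of life, mental health, loneliness and family bonding at T2-T5 as well as T1 and T6-T8, and thriving only at T1 and T6-T8. The power model in Section 9.2 also uses quality of life at T2-T5. Section 6.1.2 says otherwise: primary outcomes are asked at baseline, 1 week, 1 month and 3 months, and the session surveys are shorter, "focusing on secondary outcomes including experiences with the technology, affective states, and how they felt about their relationship with their family member".

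**Analysis.** Section 9.4.2 assigns mediation to multilevel structural equation modeling. It names no lag, no allocation of measures to mediator or outcome, no mediator-outcome confounders and no sensitivity analysis. Section 9.4.1 classes mediation models as secondary.

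**The concern.** Randomization protects the arm-to-engagement path. It does not protect the engagement-to-outcome path, which is observational. If the same construct is on both sides, or both sides are self-reported in one sitting, mood, response style and similar wording correlate them whether or not engagement changes quality of life. Once VR raises engagement, that correlation is enough to make the product of the two paths significant.

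The protocol expects that condition to hold: before stating Aim 2, Section 2.1 says Rendever should produce more engagement than video chat. At stake is the trial's explanatory claim, that VR works because it engages people (H1b, and RQ2 for the cognitive-impairment groups). As the plan stands, a positive result would not separate that explanation from a measurement artifact.

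**Working it through.** **1. Overlap by outcome**

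| Mediator component | Quality-of-life outcome (H1b) | Relationship outcome (Section 3 objective) |
|---|---|---|
| Positive affect | Overlaps (Sections 4.1, 9.1) | No direct overlap |
| Emotional closeness | No direct overlap | Overlaps (family bonding) |
| Engagement with technology and child | No direct overlap | No direct overlap |

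**2. Timing.** Under Section 1.3 and the Section 9.2 power model, mediator and outcome can come from one session. Under Section 6.1.2 the primary outcomes are not asked at sessions, but the session survey still collects affective states and relationship feelings beside experiences with the technology. Thriving is not measured at sessions under either.

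**3. Size.** The plan gives no figure for the indirect effect, so there is none to reproduce.

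Inputs from the documents: 192 dyads and about 15% attrition, 192 × 0.85 = 163. Assumed, because not stated: two-sided 0.05; arm effect on engagement d = 0, 0.2 or 0.5 SD; proportion s of the variance of each measure that is shared same-session state; one session. The true effect of engagement on the outcome, and of arm on the outcome, is zero. Mediation is declared when both paths are significant.

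- Arm-to-engagement path: z = d × √(81 × 82 / 163) = 6.38d. Power is 0.05 at d = 0, 0.25 at 0.2 (z = 1.28) and 0.89 at 0.5 (z = 3.19).
- Engagement-to-outcome path given arm: the residual correlation is s, so z = atanh(s) × √159. Rejection is 0.05, 0.24, 0.73 and 0.97 for s = 0, 10, 20 and 30%.
- The two estimates are close to independent, so the false-mediation rate is about the product:

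| d on engagement | s = 0 | 10% | 20% | 30% |
|---|---|---|---|---|
| 0 | <1% | 1% | 4% | 5% |
| 0.2 | 1% | 6% | 18% | 24% |
| 0.5 | 4% | 22% | 65% | 87% |

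Simulated trials (4,000 per setting) agree to within about one percentage point.

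**4. What lowers the rate**

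- *Averaging four sessions.* Assume an intraclass correlation of 0.5. The variance of a mean is 0.5 + 0.5/4 = 0.625 and the shared part is s/4, so the residual correlation falls to s/2.5, that is 0.04, 0.08 and 0.12. The arm path has z = 6.38 × 0.5/√0.625 = 4.04, power 0.98. The products are about 8, 17 and 32%.
- *Testing only the between-person covariance.* With four sessions, intraclass correlation 0.4-0.6, d = 0.5 and 10-30% shared state, simulation gives 4-6%.
- *Requiring a significant positive total effect as well.* The rate is 3% or less when the outcome does not change. With a true 0.2 SD outcome effect, no mediation, 192 dyads and residual correlation 0.3-0.5, 25-28% of trials show both at d = 0.5-0.8. Plain two-sample power for the outcome is 28%, so nearly every trial with a significant total effect would also report false mediation.

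**5. Does separating in time work?** With T2-T5 engagement, later outcomes and baseline adjustment, the rate returns to about 5% if only same-session state is shared. If a stable trait is shared instead (assumed loadings 0.3-0.5 on engagement and 0.8-0.9 on the outcome), it is 29-68% at d = 0.5. Adding same-session sharing with correlation 0.4 gives 90-95%.

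**The case against.** The strongest reply has five parts.

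- *Closeness is not an H1b outcome.* Correct. It overlaps only under the wider objective in Section 3.
- *Later outcomes and coded engagement exist.* Correct. T6-T8 outcomes follow the sessions, and part of the mediator is coded from recordings. A reader might infer that the plan has no time order at all, and the documents do not support that. What is missing is any statement that H1b will use that order or the coded measure.
- *The only VR-versus-control effect size in the documents is d = 0.2, where the rate is 5-24%.* Fair, although that figure was set for the outcomes. The documents give none for engagement, so the range is the honest answer.
- *H1b concerns the positive effects of VR, so it presupposes a total effect.* A reader might infer that mediation is all but guaranteed even if quality of life never changes. On this reading that fails (3% or less). But Section 9 writes no such gate, and the gate does not rescue the interpretation when VR does affect the outcome.
- *The planned multilevel model separates within- from between-person variation.* This can absorb same-session state. It does not absorb stable response style or shared content, and Section 9.4.2 does not say which level carries the indirect effect.

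A reader might also infer that H1b is untestable because engagement has no T1 value. That goes too far: the increase can be read as VR versus control, and affect and family bonding have baseline measures. The plan should say which meaning is intended.

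**Conclusion.** The point holds in conditional form. Positive affect is on both sides of H1b, the schedule allows mediator and outcome to be self-reported together, and the analysis section has no safeguard. If VR raises engagement, a significant indirect effect from the plan as written could not be taken as evidence of mediation.

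The single-session figures (22-87% at 0.5 SD, about 5-24% at 0.2 SD, at most about 5% at zero) rest on assumed effects, shared variance and alpha. They bound the problem and do not predict this trial's result. Averaging sessions or modeling the between-person part lowers them. The matter is confined to secondary, explanatory analyses.

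**What to change.** In Section 9.4, for H1b and RQ2:

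1. Use T2-T5 engagement as mediator and T6-T8 outcomes (Section 1.3 numbering), adjusted for the T1 outcome.
2. List the measures on each side. Drop positive affect from the mediator when the outcome is affect, and closeness when it is relationship quality or family bonding.
3. For residents, make the already planned coded engagement the main mediator.
4. Label same-session indirect effects descriptive.
5. Add a sensitivity analysis that varies the residual mediator-outcome correlation and reports the value at which the indirect effect vanishes. This is essential, because lagging does not remove a shared stable trait or response style.
6. State that an increase in in-session engagement means VR versus control.
7. Reconcile Section 6.1.2 with the Section 1.3 schedule and the Section 9.2 power model on which outcomes are asked at sessions.

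The cost is SAP wording and model set-up, with no new data. The downside is a smaller and less precise indirect effect. Section 1.2 already reports attrition for the whole trial, so the amendment should say whether it was made before outcome data were examined.
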